21-30 = extremely large effect on patient’s life

This categorization will not be utilized in the analysis.

Because Q7 has a sub-question (referred to as Q7a here) after the leading yes/no question, some clarifying rules for scoring are provided:

- If Q7 is marked as “yes”, a score of 3 is given regardless of the responses to Q7a.
- If Q7 is marked as “no”, “not relevant”, or is missing and Q7a is “A lot”, a score of 2 is given.
- If Q7 is marked as “no”, “not relevant”, or is missing and Q7a is “A little”, a score of 1 is given.
- If Q7 is marked as “no”, “not relevant”, or is missing and Q7a is “Not at all”, a score of 0 is given.
- If Q7 is marked as “no” or “not relevant” and Q7a is missing, a score of 0 is given.
- If Q7 is missing and Q7a is missing, Q7 is considered unanswered (see below for details on how this impacts the DLQI total score).

If 1 question is left unanswered, this is scored 0 and the scores are summed and expressed as usual out of a maximum of 30. If 2 or more questions are left unanswered, the questionnaire is not scored.

Change from Baseline in DLQI total score is defined as Week 16 DLQI total score minus Baseline DLQI total score.

8.3.3.1 Primary analysis of change from Baseline in DLQI Total score at Week 16

Missing data imputation described in Section 4.2.1.2 will be applied.

Change from Baseline in DLQI total score will be presented by treatment group. The analysis model will be based on an ANCOVA with fixed effects of treatment, Hurley Stage at Baseline, Baseline antibiotic use and Baseline value as a covariate. The least square mean (LSM), standard error (SE), and 95% CI for the LSM will be presented by treatment group. For the comparison between placebo and bimekizumab: the difference between the LSM, the associated 97.5% CI for the contrasts, and the corresponding p-value will be presented. If one dose regimen is tested at the 0.05 significance level as determined in Section 4.5, then the confidence interval will be 95% instead of 97.5% for that dose with a corresponding $Z_{\alpha/2}$ of 1.96. Estimand and intercurrent event details are specified in Table 8–2.

8.3.3.2 Sensitivity analysis of change from Baseline in DLQI Total score at Week 16

A sensitivity analysis using the same analysis model as in Section 8.3.3.1 will be used, based on observed data. Estimand and intercurrent event details are specified in Table 8–2.

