8.4.15 Hidradenitis Suppurativa Quality of Life (HiSQOL)

The HiSQOL includes 17 items assessed using a 7-day recall period, grouped in 3 subscales: symptoms, psychosocial, activities and adaptation.

The assessment of each item of the HiSQOL is as follows:

Table 8–5: Hidradenitis Suppurative Quality of Life

HiSQOL Scoring	
Response	Score
Unable to do, due to my HS	4
Extremely	4
Very Much	3
Moderately	2
Slightly	1
Not at all	0
I normally do not do this, HS did not influence	0
I am not sexually active	0
I do not work or study	0
Unanswered	0

The HiSQOL total score is calculated by adding the score of each question. The maximum score is 68, and the minimum score is 0.

Subscale scores will be summarized for each of the 3 subscales. The maximum scores for the subscales are 16 (symptoms), 20 (psychosocial), and 32 (activities and adaptations), and the minimum score is 0 for all subscales.

For all scores, the higher the score, the more quality of life is impaired.

Summary statistics of the actual values and change from Baseline values will be used to summarize HiSQOL domain and total scores for each visit by treatment group. The table will display descriptive statistics for the Baseline, followed by descriptive statistics for the change from Baseline for all visits.

Additionally, change from Baseline in each HiSQOL subscale will be evaluated by treatment group at Week 16 and at Week 48 via continuous eCDF plots showing the absolute change from Baseline on the horizontal axis and the cumulative percent of participants experiencing that change on the vertical axis.

Missing data for the continuous change from Baseline will be handled by using MI via the MCMC and monotone regression method specified in Section 4.2.1.3. The imputed HiSQOL total score will be derived based on the imputed subscales.

The number and percentage of participants that complete the HiSQOL will be calculated for each visit by treatment group. The percentage will be based on the number of participants in the RS (or MS, as appropriate). The summary will be repeated where the percentage is based on the subset of participants who complete each particular visit. A participant will be considered a completer at a visit if the total score is calculated at that visit.

A by-participant listing of the HiSQOL questionnaire, HiSQOL responses, domain and total scores and change from Baseline will be provided.

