- 6 = degree problem affected regular activities

Scores:

- Percent work time missed due to problem: $[\text{Q2 hours}/(\text{Q2 hours} + \text{Q4 hours})] * 100$
- Percent impairment while working due to problem: $[\text{Q5 score}/10] * 100$
- Percent overall work impairment due to problem: $[\text{Q2 hours}/(\text{Q2 hours} + \text{Q4 hours}) + [(1 - (\text{Q2 hours}/(\text{Q2 hours} + \text{Q4 hours})) \times (\text{Q5 score}/10)]] * 100$
- Percent activity impairment due to problem: $[\text{Q6 score}/10] * 100$

A negative number will indicate a reduction in the score/improvement for participants.

The change from Baseline score is derived as post Baseline score minus Baseline score. A negative change score indicates a reduction in the score/improvement for the participant.

Summary statistics of the actual values and change from Baseline values will be used to summarize WPAI-SHP for each visit by treatment group. The table will display descriptive statistics for the Baseline, followed by descriptive statistics for the change from Baseline for all visits.

Missing data for the continuous change from Baseline will be handled by using MI via the MCMC and monotone regression method specified in Section 4.2.1.3.

The number and percentage of participants that complete the WPAI-SHP will be calculated for each visit by treatment group. The percentage will be based on the number of participants in the RS. The summary will be repeated where the percentage is based on the subset of participants who complete each particular visit. A participant will be considered a completer at a visit if the percentages in each dimension are calculated at that visit.

A by-participant listing of the WPAI-SHP questionnaire, WPAI-SHP domains and change from Baseline will be provided.

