10.4.3.5 Patient Health Questionnaire (PHQ)-9 scores

The PHQ-9 is a multipurpose instrument for screening, diagnosing, monitoring, and measuring the severity of depression. The PHQ-9 scores for depression range from 0 to 27 with higher scores indicating worse state. A score of 5 to 9 is considered to be minimal symptoms of depression. If any of the 9 questions are missing, then the score is treated as missing. A score of 10 to 14 is considered minor depression, dysthymia, or mild major depression. A score of 15 to 19 is considered to indicate moderately severe major depression, and a score ≥ 20 is considered to be severe major depression.

Change from Baseline in PHQ-9 is derived as post-Baseline score minus Baseline score.

A summary of the absolute and change from Baseline value will be presented by treatment group and visit.

The percentage of study participants with scores below 5, between 5 and 9, between 10 and 14, between 15 and 19, and greater than or equal to 20 in PHQ-9 will be summarized as a shift from Baseline by visit and treatment group based on observed values.

The percentage of study participants with scores ≥ 15 at any post-Baseline visit and the number and percentage of study participants with scores ≥ 20 at any post-Baseline visit will be summarized by treatment group based on observed values. This summary will also include the percentage of study participants with increase from baseline ≥ 5 at any post-Baseline visit.

The number and percentage of participants that complete the PHQ-9 will be calculated for each visit by treatment group. The percentage will be based on the number of participants in the RS. The summary will be repeated where the percentage is based on the subset of participants who complete each particular visit.

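### HiSQOL scores any number of unanswered items as 0, and the WPAI-SHP completion rule can never be met by a participant without a job

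*SAP*

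**What the plan says.** **HiSQOL, Section 8.4.15.** "The HiSQOL includes 17 items assessed using a 7-day recall period", in three subscales with maxima 16, 20 and 32. For the total, "The maximum score is 68, and the minimum score is 0", and higher is worse. Table 8-5 assigns 0 to 'Unanswered'. It assigns the same 0 to 'Not at all' and to three options for activities that do not apply to the respondent. The scoring rule is: "The HiSQOL total score is calculated by adding the score of each question". No minimum number of answered items is given for the total or for any subscale. The section plans multiple imputation for missing change from Baseline, with the imputed total built from imputed subscales. Completion is defined by: "A participant will be considered a completer at a visit if the total score is calculated at that visit".

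**Other instruments in the same SAP.** DLQI, Section 8.3.3: "If 2 or more questions are left unanswered, the questionnaire is not scored". PHQ-9, Section 10.4.3.5: "If any of the 9 questions are missing, then the score is treated as missing".

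**WPAI-SHP, Section 8.4.21.** Q1 records whether the participant is employed. Three of the four dimensions are computed from Q2, Q4 and Q5 (hours missed, hours worked, effect on productivity at work); the fourth uses Q6 (regular activities). On missing data: "Missing data for the continuous change from Baseline will be handled by using MI via the MCMC and monotone regression method". On completion: "A participant will be considered a completer at a visit if the percentages in each dimension are calculated at that visit". Table 4-2 gives allowable imputation ranges for the work variables by name.

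**The concern.** In HiSQOL, a participant to whom an item does not apply has a response option that says so. An unanswered item is therefore true non-response, yet it receives the best possible score. Because the blank already holds a value, nothing remains to be imputed on a returned form, and the total always exists. The SAP thus has no means of recognising a poorly completed form: its score is distorted, and the completion table reports it as complete.

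In WPAI-SHP the problem is that absence of a job is not distinguished from absence of data. Completion is judged on four percentages, three of which cannot exist for someone who is not working, and the item that would tell the two situations apart is never used.

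What is at stake is the accuracy of the HiSQOL summaries and the subscale distribution plots at Weeks 16 and 48, the meaning of the WPAI work summaries, and two completion tables. HiSQOL completion can only be overstated and WPAI completion only understated.

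**Working it through.** **1. The plan's own HiSQOL range.** Inputs from Section 8.4.15: 17 items, maximum item score 4, subscale maxima 16, 20 and 32.
- 17 × 4 = 68, and 16 + 20 + 32 = 68. The stated maximum is reproduced.
- The subscales hold 16/4 = 4, 20/4 = 5 and 32/4 = 8 items.

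**2. Effect of blanks on one form.** If *k* items with true mean score *m* are left blank, the total falls by *k* × *m*.
- True total 30 spread evenly: *m* = 30/17 = 1.76. With 8 blanks the loss is 8 × 30/17 = 14.1, so the form scores 15.9. If the 8 blanks are the whole activities subscale, that subscale reads 0 instead of 14.1.
- True item score 2 (true total 34):

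| Blanks | Scored total | Points lost |
|---|---|---|
| 0 | 34 | 0 |
| 1 | 32 | 2 |
| 2 | 30 | 4 |
| 5 | 24 | 10 |
| 8 | 18 | 16 |
| 17 | 0 | 34 |

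**3. Direction for change from Baseline.** Take a participant whose true total stays at 30.
- 8 blanks after Baseline: 15.9 − 30 = −14.1, a false improvement.
- 8 blanks at Baseline: 30 − 15.9 = +14.1, a false worsening.

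**4. Effect on an arm mean.** The share of affected forms is not in the SAP, so these are illustrations.
- 5% of post-Baseline forms with 8 blanks at a true total of 30: 0.05 × 14.1 = 0.7 points.
- At item score 2: 5% with 4 blanks, 0.4; 5% with 8 blanks, 0.8; 10% with 8 blanks, 1.6.

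**5. WPAI completion ceiling.** If a share *u* is not employed, completion cannot exceed 1 − *u*, even with every form fully answered. The SAP gives no employment rate. For an assumed *u* of 10% to 50% of about 490 randomized, 49 to 245 participants can never be completers, and the ceiling runs from 90% down to 50%.

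**6. WPAI imputation.** Section 4.2.1.3 sends missing values of other continuous endpoints to multiple imputation, and no text excludes work scores that do not apply. However, Section 4.2.2.1 derives change from the observed Baseline value. A participant with no job at Baseline has no observed Baseline work score, and so no imputed change. For change, exposure is mainly those employed at Baseline who stop working during the trial. For the rest it lies in the summaries of actual values, which Section 8.4.21 also plans.

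**The case against.** The stakes are low. Both instruments are listed among the other efficacy endpoints (Section 2.2.1.3). They are outside the testing sequence of Section 4.5 and absent from the nominal p-value list in Section 8.5. This stands, and it sets the severity.

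Scoring a blank as 0 is not peculiar to HiSQOL: DLQI Table 8-3 does so too, for a single blank. This also stands. What differs is the missing cap, not the zero.

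An electronic form might prevent skipped items, in which case the HiSQOL rule would rarely operate. The data-capture design is not shown, so frequency is unknown. But Table 8-5 itself provides for unanswered items, and the rule it sets for them is wrong once there are many.

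Section 8.4.21 refers to the instrument's own scoring rules, which may treat people without a job separately. That could settle scoring. It would not mend the completion rule, which the SAP states itself.

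A reader might infer that every participant without a job receives imputed work scores; at an assumed 30% to 45% that would be 147 to 220 of 490. The documents do not support this. No sentence says that a score which does not apply is to be imputed, and change requires an observed Baseline value. A reader might also infer that HiSQOL non-response always favours whichever arm skips more. Step 3 of the working shows that the direction depends on when the blanks occur as well as in which arm.

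**Conclusion.** The HiSQOL defect is explicit in Section 8.4.15: there is no cap on blanks, so a poorly completed form is scored too low, escapes imputation and counts as complete. Its size on one form can be large (about 14 of 68 points in the example). Its size on an arm mean cannot be stated, because the share of affected forms is unknown.

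The WPAI completion defect is equally explicit and does not depend on how the imputation text is read; only its size rests on an assumed employment rate. The WPAI imputation issue is narrower: the SAP does not say where the work dimensions apply. For change from Baseline this mainly concerns participants who stop working; otherwise it concerns the actual-value summaries.

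Severity is minor. Nothing here supports doubt about a primary, secondary or nominal test.

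**What to change.** **HiSQOL.** Add a cap to Section 8.4.15 and a footnote to the 'Unanswered' row of Table 8-5. One option, following the DLQI rule: a single unanswered item is scored 0; with 2 or more, every subscale containing a blank and the total are set to missing and passed to imputation. Imputing at subscale level fits the existing plan to build the total from imputed subscales. Carrying a 10-item threshold to a 17-item instrument is a judgement the sponsor should confirm. Define completers by the same rule. Keep 0 for the three response options that mean the activity does not apply.

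**WPAI-SHP.** Define completion as Q1 and Q6 answered, plus the work items if employed. State that the three work dimensions are summarized and imputed only where Q1 shows that they apply, and display the number employed at each visit. Because employment after Baseline may itself respond to disease or treatment, that count should stand beside the work results. Say also which Q1 answer governs when a form is missing.

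**Cost.** SAP wording and small programming changes on data already collected. Somewhat more HiSQOL values go to imputation, and fewer participants contribute to the WPAI work summaries.

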8.4.16 Patient Global Impression of HS Severity (PGI-S-HS)

The PGI-S-HS is a single item to assess study participants perceptions of the overall severity of HS over the past 7 days (none, mild, moderate, severe, very severe).

The number and percentage of participants with each response will be summarized for each visit by treatment group based on OC data.

The number and percentage of participants that complete the PGI-S-HS will be calculated for each visit by treatment group. The percentage will be based on the number of participants in the RS. The summary will be repeated where the percentage is based on the subset of participants who complete each particular visit. A participant will be considered a completer at a visit if the response is nonmissing at that visit.

8.4.17 Patient Global Impression of Change in HS Severity (PGI-C-HS)

The PGI-C-HS is a single item to assess study participants perception of the change in HS since they started taking the study medication (much better, a little better, no change, a little worse, much worse).

The number and percentage of participants with each response will be summarized for each visit by treatment group based on OC data.

The number and percentage of participants that complete the PGI-C-HS will be calculated for each visit by treatment group. The percentage will be based on the number of participants in the RS (or MS, as appropriate). The summary will be repeated where the percentage is based on the subset of participants who complete each particular visit. A participant will be considered a completer at a visit if the response is nonmissing at that visit.

8.4.18 Patient Global Impression of Severity of Skin Pain (PGI-S-SP)

The PGI-S-SP is a single item to assess study participants' perceptions of the severity of their skin pain from their HS lesions, over the past 7 days (none, mild, moderate, severe, very severe).

The number and percentage of participants with each response will be summarized for each visit by treatment group based on OC data.

The number and percentage of participants that complete the PGI-S-SP will be calculated for each visit by treatment group. The percentage will be based on the number of participants in the RS (or MS, as appropriate). The summary will be repeated where the percentage is based on the subset of participants who complete each particular visit. A participant will be considered a completer at a visit if the response is nonmissing at that visit.

8.4.19 Patient Global Impression of Change in Severity of Skin Pain (PGI-C-SP)

The PGI-C-SP is a single item to assess study participants' perceptions of change in their skin pain from their HS lesions, since they started taking the study medication (much better, a little better, no change, a little worse, much worse).

The number and percentage of participants with each response will be summarized for each visit by treatment group based on OC data.

The number and percentage of participants that complete the PGI-C-SP will be calculated for each visit by treatment group. The percentage will be based on the number of participants in the RS. The summary will be repeated where the percentage is based on the subset of participants who complete each particular visit. A participant will be considered a completer at a visit if the response is nonmissing at that visit.

8.4.20 Euro-Quality of Life 5-Dimensions, 3 levels (EQ-5D-3L)

The EQ-5D-3L comprises 5 questions on mobility, self-care, pain, usual activities, and psychological status with 3 possible answers for each item (1=no problem, 2=moderate problem, 3=severe problem). In addition, there is a VAS to indicate the general health status with 100 indicating the best health status.

Change from Baseline in EQ-5D-3L VAS scores is defined as Post-Baseline EQ-5D-3L VAS score minus Baseline EQ-5D-3L VAS score.

Responses to EQ-5D-3L will be summarized based on OC only as primary analysis. No imputation is applied to responses to EQ-5D-3L but is applied to EQ-5D-3L VAS scores.

Changes from Baseline in EQ-5D-3L VAS will be summarized using descriptive statistics by treatment group and visit. The table will display descriptive statistics for the Baseline, followed by descriptive statistics for the change from Baseline for all visits.

The number and percentage of participants with each response in the EQ-5D-3L will be summarized for each visit by treatment group based on OC data.

The number and percentage of participants that complete the EQ-5D-3L will be calculated for each visit by treatment group. The percentage will be based on the number of participants in the RS. The summary will be repeated where the percentage is based on the subset of participants who complete each particular visit. A participant will be considered a completer at a visit if each of the domains and VAS are completed at that visit.

8.4.21 Work Productivity and Activity Impairment Questionnaire–Specific Health Problem (WPAI-SHP) v2.0 adapted to HS scores

The WPAI-SHP V2.0 is a patient-reported questionnaire that assesses study participant's employment status, work absenteeism, work impairment while working (presenteeism), overall work, and daily activity impairment attributable to a specific health problem. It has been used in several clinical studies of biologic therapy in participants with plaque PSO.

Five out of 6 items of the WPAI-SHP are regrouped into the 4 dimensions, with scores expressed as percentage, where higher numbers indicate greater impairment and less productivity, ie, worse outcomes, as described in the WPAI-SHP scoring rules.

The scoring rules for the WPAI-SHP are as follows:

Questions:

- 1 = currently employed
- 2 = hours missed due to specified problem
- 3 = hours missed other reasons
- 4 = hours actually worked

- 5 = degree problem affected productivity while working
- 6 = degree problem affected regular activities

Scores:

- Percent work time missed due to problem: $[\text{Q2 hours}/(\text{Q2 hours} + \text{Q4 hours})] * 100$
- Percent impairment while working due to problem: $[\text{Q5 score}/10] * 100$
- Percent overall work impairment due to problem: $[\text{Q2 hours}/(\text{Q2 hours} + \text{Q4 hours}) + [(1 - (\text{Q2 hours}/(\text{Q2 hours} + \text{Q4 hours})) \times (\text{Q5 score}/10)]] * 100$
- Percent activity impairment due to problem: $[\text{Q6 score}/10] * 100$

A negative number will indicate a reduction in the score/improvement for participants.

The change from Baseline score is derived as post Baseline score minus Baseline score. A negative change score indicates a reduction in the score/improvement for the participant.

Summary statistics of the actual values and change from Baseline values will be used to summarize WPAI-SHP for each visit by treatment group. The table will display descriptive statistics for the Baseline, followed by descriptive statistics for the change from Baseline for all visits.

Missing data for the continuous change from Baseline will be handled by using MI via the MCMC and monotone regression method specified in Section 4.2.1.3.

The number and percentage of participants that complete the WPAI-SHP will be calculated for each visit by treatment group. The percentage will be based on the number of participants in the RS. The summary will be repeated where the percentage is based on the subset of participants who complete each particular visit. A participant will be considered a completer at a visit if the percentages in each dimension are calculated at that visit.

A by-participant listing of the WPAI-SHP questionnaire, WPAI-SHP domains and change from Baseline will be provided.

